#### **3.2.1.2 Monitoring of dose administration**

Subjects will be monitored before, during and after the infusion with assessment of vital signs at the times specified in the Schedule of Assessment. Subjects are monitored (pulse rate, blood pressure) every 30 minutes during the infusion period (including times where infusion rate is slowed or temporarily stopped).

In the event of a  $\leq$ Grade 2 infusion-related reaction, the infusion rate of study drug may be decreased by 50% or interrupted until resolution of the event (up to 4 hours) and re-initiated at 50% of the initial rate until completion of the infusion. For subjects with a  $\leq$ Grade 2 infusion-related reaction, subsequent infusions may be administered at 50% of the initial rate. Acetaminophen and/or an antihistamine (e.g., diphenhydramine) or equivalent medications per institutional standard may be administered at the discretion of the investigator. If the infusion-related reaction is Grade 3 or higher in severity, study drug will be discontinued. The standard infusion time is one hour, however if there are interruptions during infusion, the total allowed time from infusion start to completion of infusion should not exceed 4 hours at room temperature, with maximum total time at room temperature not exceeding 4 hours (otherwise requires new infusion preparation).

As with any antibody, allergic reactions to dose administration are possible. Appropriate drugs and medical equipment to treat acute anaphylactic reactions must be immediately available, and study personnel must be trained to recognize and treat anaphylaxis. The study site must have immediate access to emergency resuscitation teams and equipment in addition to the ability to admit subjects to an intensive care unit if necessary.

### **3.2.2 Vicineum™**

#### **3.2.2.1 Doses And Treatment Regimens**

The initial dose of vicineum is 30 mg in 50 mL of saline (Dose level 1). Vicineum will be instilled through a catheter into the bladder. Subjects will be instructed to hold study drug in the bladder for 2 hours, and asked to refrain from fluid intake to reduce urine flow during this period. After complete administration of the Vicineum dose, the catheter may be clamped and remain in for the 2-hour dwell time, or may be removed, per the discretion of the investigator.

Subjects will be encouraged, when physically possible, to be upright (sitting or standing), prone, supine, and in the left and right lateral decubitus positions, for at least 15 minutes each, in any order. If physically unable, this should be recorded in the CRF. At the end of 2-hour period, the catheter will be unclamped and the bladder will be drained (if the catheter remained in place) or the subject will void to empty the bladder.

Study Phase	Treatment Regimen
Induction Phase (Weeks 1-12)	One intravesical dose of Vicineum in 50 mL of saline instilled once weekly for a total of 12 weeks.
Maintenance Phase (up to Week 104)	One intravesical dose of Vicineum 50 mL saline instilled once every other week for 12 months from the start of the Induction phase. Please note, at the end of each maintenance cycle there is a 2 week window in order to allow the patients sufficient time to recover from biopsies prior to continuing treatment. Refer to the schema for a detailed description of Vicineum administration weeks. If remain disease-free, therapy can be continued for up to 24 months (Week 104) from the start of the Induction Phase.

### 3.3 DOSE MODIFICATIONS

#### 3.3.1 Durvalumab

Following any biopsy or TURBT, study drug must be interrupted for a maximum of 2 weeks before restarting Durvalumab treatment.

For adverse events (AEs) that are considered at least partly due to administration of durvalumab outside of the DLT evaluation period, the following dose adjustment guidance may be applied:

- Treat each of the toxicities with maximum supportive care (including holding the agent suspected of causing the toxicity where required).
- If the symptoms promptly resolve with supportive care, consideration should be given to resuming the same dose of durvalumab along with appropriate continuing supportive care.
- If medically appropriate, dose modifications are permitted for durvalumab. All dose modifications should be documented with clear reasoning and documentation of the approach taken (see [Appendix C](#)).

In addition, there are certain circumstances in which durvalumab should be permanently discontinued (see [Appendix C](#)). In circumstances where subjects cannot tolerate durvalumab or do not meet retreatment criteria to receive either drug, subjects will be taken off protocol therapy.

Following the first dose of durvalumab, subsequent administration of durvalumab can be modified based on toxicities observed (see [Appendix C](#)).

Based on the mechanism of action of durvalumab leading to T-cell activation and proliferation, there is the possibility of observing immune related Adverse Events (irAEs) during the conduct of this study. Potential irAEs include immune-mediated enterocolitis, dermatitis, hepatitis, and endocrinopathies. Subjects should be monitored for signs and symptoms of irAEs. In the absence of an alternate etiology (e.g., infection or PD) signs or symptoms of enterocolitis, dermatitis, hepatitis, and endocrinopathy should be considered to be immune-related.

Dose modification recommendations and toxicity management guidelines for immune-mediated reactions, for infusion-related reactions, and for non-immune-mediated reactions are detailed in [Appendix C](#).

### 3.3.2 Vicineum

Following any biopsy or TURBT, study drug must be interrupted for a minimum of 1 week and maximum of 2 weeks before restarting Vicineum treatment. Patients who develop low grade papillary disease will be allowed to stay on trial. In November 2016, the FDA published a draft guidance for trials involving patients with BCG-unresponsive disease in which only high-risk disease counts as a recurrence or an event. In this clinical setting, low-risk disease would lead to transurethral resection while high-risk disease would lead to cystectomy, which is a much different clinical outcome. Therefore, in this trial, low grade recurrences will be documented but will not count as a trial-ending recurrence or event. Furthermore, low grade recurrences are considered to be downstaging of disease since the inclusion criteria requires patients with high grade disease.

Study drug administration must be postponed if a subject develops any Grade 3 or greater adverse event. Study treatment may resume when the AE returns to  $\leq$  Grade 1 or baseline or sooner if there is agreement between the investigator and the sponsor. Study treatment may be postponed at the discretion of the investigator for unrelated AEs, if this is considered in the best interest of the subject. If the causal relationship between Vicineum and an AE is initially uncertain, study drug should be interrupted until that determination is made. Also study treatment may be postponed for lower grade AEs at the investigator discretion if considered in the best interest of the subject.

The following specific criteria will be used for holding Vicineum dosing based on serum creatinine and calculation of creatinine clearance:

Baseline Creatinine	Criteria for Holding Vicineum Treatment*	
	Serum Creatinine	Creatinine Clearance
<1.0 mg/dl or <88 $\mu$ mol/L	>1.5 mg/dl or >133 $\mu$ mol/L	<40 ml/min or a decrease of 25% from baseline
$\geq$ 1.0 mg/dl or $\geq$ 88 $\mu$ mol/L	Increase to $>2 \times$ Baseline Value	<40 ml/min or a decrease of 25% from baseline

\*Vicineum dosing should be held if either the serum creatinine or the creatinine clearance criteria, as defined in this table, are met.

If changes in renal function are noted, the investigator should evaluate the subject for the etiology of these changes. Vicineum treatment may be resumed upon improvement or stabilization at creatinine of  $\leq 2 \times$  baseline or  $\leq 2 \times$  ULN.

- Vicineum dosing must be held for any subject whose AST or ALT doubles from their baseline value and is  $\geq 2 \times$  ULN; OR for a bilirubin  $\geq 2 \text{ mg/dl}$  ( $\geq 34 \text{ } \mu\text{mol/L}$ ). However, if Grade 2 hyperbilirubinemia occurs during the DLT evaluation period, then a DLT is present and treatment will be permanently discontinued and patient will be removed from study. The investigator should evaluate subjects for the etiology of any changes in these values. Vicineum treatment may be resumed upon improvement or stabilization of AST and ALT of  $\leq 2 \times$  baseline or  $\leq 2 \times$  ULN; OR for a bilirubin  $\leq 2 \text{ mg/dl}$  ( $\leq 34 \text{ } \mu\text{mol/L}$ ) provided that Grade 2 hyperbilirubinemia did not occur.
- The investigator should consider holding Vicineum treatment for patients with a clinically significant UTI requiring antibiotic therapy until improvement. Investigators should also consider holding Vicineum treatment for patients with grade II hematuria.

Missed doses should not be made up. In the Maintenance Phase, dosing should be restarted as soon as there is AE resolution i.e., treatment should not be postponed longer in order to align with the initial every-other-week schedule.

If study treatment is postponed longer than 3 weeks, the investigator should consider whether the subject should remain on treatment.

In circumstances where subjects cannot tolerate Vicineum or do not meet retreatment criteria to receive either drug, subjects will be taken off protocol therapy.

The reasons and details relevant to the subject postponement and/or discontinuation of study treatment must be recorded on the CRF. The Investigator must notify Sesen Biotherapeutics if study treatment is discontinued.

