We would like to continue the drug-combination trial since our preliminary interim data analysis shows a 40% 12 week response rate (5/12 patients) with half of them showing a  $>12$  month sustained response. We hypothesize that the prolonged response might be related to the systemic therapy (Durvalumab) administration. Also, most of the treatment related AEs are irritative voiding symptoms and most of them are grade 3 or lower, suggesting that the treatment is tolerated well thus far. Combination Therapy Dose Justification

In the single-agent phase I Vicineum study, there were no dose-limiting toxicities (DLTs) and no MTD was determined. Only 2 subjects of 64 had detectable plasma Vicineum levels and these were very near the lower level of quantitation. Durvalumab has been extensively studied in Phase I and Phase II and the recommended dose and safety profile has been established. For these reasons, the initial dose level for the combination will be the standard doses for both drugs. The FDA approved dose for durvalumab is currently 10mg/kg every 2 weeks and this amounts to 750 mg every 2 weeks for an average 75 kg individual. Based on pre-clinical data, there is no difference in exposure between weight based Q2W dosing and fixed dose Q4W dosing. Therefore, we are administering 1500 mg every 4 weeks instead of 750 mg every 2 weeks for ease and dosing convenience.

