- Serum bilirubin  $\leq$  1.5  $\times$  institutional upper limit of normal (ULN).
- AST (SGOT)/ALT (SGPT)  $\leq$  2.5  $\times$  institutional ULN
- Creatinine CL $>40$  mL/min by the Cockcroft-Gault formula (Cockcroft and Gault 1976) or by 24-hour urine collection for determination of creatinine clearance:

Males:

$$\text{Creatinine CL} = \frac{\text{Weight (kg)} \times (140 - \text{Age})}{72 \times \text{serum creatinine (mg/dL)}}$$

Females:

$$\text{Creatinine CL} = \frac{\text{Weight (kg)} \times (140 - \text{Age})}{72 \times \text{serum creatinine (mg/dL)}} \times 0.85$$

2.1.1.8 Female subjects must either be of non-reproductive potential (i.e., post-menopausal as described below) OR history of surgical sterilization (hysterectomy, bilateral tubal ligation, or bilateral oophorectomy) or must have a negative serum pregnancy test upon study entry.

- Women <50 years of age would be considered post-menopausal if they have been amenorrheic for 12 months or more following cessation of exogenous hormonal treatments and if they have luteinizing hormone and follicle-stimulating hormone levels in the post-menopausal range for the institution
- Women ≥50 years of age would be considered post-menopausal if they have been amenorrheic for 12 months or more following cessation of all exogenous hormonal treatments, had radiation-induced menopause with last menses >1 year ago, or had chemotherapy-induced menopause with last menses >1 year ago

2.1.1.9 The effects of Vicineum and durvalumab on the developing human fetus are unknown. Females of childbearing potential and men who are sexually active must use a highly effective method of contraception (including abstinence, intrauterine system or intrauterine device contraceptive implant, hormonal, female or partner sterilization or menopause as defined in 2.1.1.8) and a second form of barrier contraception during study treatment and for 120 days after the last dose of study drug. Note: partner's use of the same methods of contraception (barrier, hormonal, intrauterine device [IUD], surgical sterilization) is also acceptable. Should a woman become pregnant or suspect she is pregnant while she or her partner is participating in this study, she should inform her treating physician immediately.

2.1.1.10 Written informed consent obtained from the subject prior to performing any protocol-related procedures

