#### 14.2.2.3 Phase 3 trial (Study No. VB4-845-02-III A)

**Table 3.** Treatment-Emergent Adverse Events Considered Related to Vicineum occurring in  $\geq 5\%$  of subjects, VB4-845-02-III A

Adverse Event	Grade 1 – 2	Grade 3 – 4	Grade 5	Total
Any Event Related to Vicineum	61 (46%)	4 (3%)	1 (1%)	66 (50%)
Renal and Urinary Disorders	45 (34%)	1 (1%)	1 (1%)	47 (35%)
Dysuria	18 (14%)	0	0	18 (14%)
Haematuria	17 (13%)	0	0	17 (13%)
Pollakiuria	15 (11%)	0	0	15 (11%)
Micturition Urgency	15 (11%)	0	0	15 (11%)
General Disorders and Administration Site Conditions	12 (9%)	0	0	12 (9%)
Fatigue	10 (8%)	0	0	10 (8%)
Gastrointestinal Disorders	9 (7%)	0	0	9 (7%)
Infections and Infestations	15 (11%)	2 (2%)	0	17 (13%)
Urinary Tract Infection	14 (11%)	2 (2%)	0	16 (12%)
Investigations	7 (5%)	3 (2%)	0	10 (8%)

Note: Treatment-emergent adverse events were assessed as possibly, probably, or definitely related to study treatment per Investigator

Data Source: VB4-845-02-III A Interim CSR Table 28

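### Section 3.3.2: the renal hold and restart rules for Vicineum conflict, because restart has no clearance condition and can be met below the protocol's own 40 ml/min limit

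*Combined protocol and SAP*

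**What the plan says.** The hold table in protocol section 3.3.2 has two rows by baseline creatinine.

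- Baseline below 1.0 mg/dl: hold when serum creatinine exceeds 1.5 mg/dl.
- Baseline 1.0 mg/dl or more: hold when it exceeds 2 x baseline.
- Both rows: hold when clearance is "<40 ml/min or a decrease of 25% from baseline".

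The footnote makes either column sufficient: "Vicineum dosing should be held if either the serum creatinine or the creatinine clearance criteria, as defined in this table, are met".

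The text below the table asks the investigator to look for the cause and then gives the restart rule: "Vicineum treatment may be resumed upon improvement or stabilization at creatinine of" no more than 2 x baseline or no more than 2 x ULN. Clearance is not mentioned. No other section sets a renal restart limit for Vicineum.

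Inclusion criterion 2.1.1.7 requires clearance above 40 "mL/min by the Cockcroft-Gault formula", or by 24-hour urine collection.

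**The concern.** The hold uses clearance and serum creatinine; the restart uses serum creatinine alone, at a looser level. A patient held on clearance, with creatinine between 1.33 and 2 times baseline, already meets the restart number on the day the hold begins. Only stabilization remains to be shown.

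Once such a patient restarts below 40 ml/min, the table's hold criterion is still met. The acute care panel is drawn weekly in induction (section 3.4), so the site must either hold again at the next panel or treat the clearance limit as void. The protocol does not say which, and different patients could be handled differently.

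What is at stake is dosing at a renal function at which the same section stops dosing and at which the patient could not have enrolled, in a trial whose primary objective is safety and tolerability.

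**Working it through.** **Inputs.** The hold and restart limits come from 3.3.2; the entry limit and formula from 2.1.1.7. The formula is clearance = weight x (140 - age) / (72 x serum creatinine), times 0.85 for women. The plan states no figure of its own to reproduce.

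**Clearance column.** At fixed weight and age, clearance is inversely proportional to creatinine. If creatinine is m times baseline, clearance is CL0 / m.

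- A 25% fall occurs at m = 1 / 0.75 = 1.33.
- The 40 ml/min limit is reached at m = CL0 / 40. It comes before the 25% fall when CL0 < 40 / 0.75 = 53.3.
- At the restart limit m = 2, clearance is CL0 / 2, which is below 40 when CL0 < 80.

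| Baseline clearance (ml/min) | Hold begins | Below 40 when creatinine exceeds | Clearance at 2 x baseline |
|---|---|---|---|
| 45 | above 1.125 x | 1.125 x | 22.5 |
| 50 | above 1.25 x | 1.25 x | 25 |
| 60 | 1.33 x (45 ml/min) | 1.5 x | 30 |
| 70 | 1.33 x (52.5 ml/min) | 1.75 x | 35 |
| 79 | 1.33 x (59.25 ml/min) | 1.975 x | 39.5 |
| 80 | 1.33 x (60 ml/min) | 2 x | 40 (not below) |

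**Worked patient.** A man of 75 kg, the average weight used in the dose justification ("this amounts to 750 mg every 2 weeks for an average 75 kg individual"). Age 75 and creatinine 1.1 mg/dl are assumptions.

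- Baseline clearance: 75 x 65 / (72 x 1.1) = 61.6.
- Hold from 1.1 / 0.75 = 1.47 mg/dl, where clearance is 46.2.
- Below 40 ml/min above 75 x 65 / (72 x 40) = 1.69 mg/dl.
- Restart limit on the baseline limb: 2 x 1.1 = 2.2 mg/dl, where clearance is 61.6 / 2 = 30.8. The serum hold (above 2.2) is not met there, but the clearance hold is.

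**Serum column, baseline below 1.0 mg/dl.** The hold is above 1.5 mg/dl and the restart limit is 2 x baseline. These overlap when 2 x baseline > 1.5, that is, baseline > 0.75. At baseline 0.9, a value of 1.6 is held (above 1.5) and also restartable (at or below 1.8). For baseline 1.0 or more, the serum hold and the 2 x baseline limb are complementary and do not conflict.

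**The 2 x ULN alternative.** Joined by 'or', the working ceiling is the larger of the two limits, so it is 2 x ULN whenever baseline is below ULN. The documents give no ULN; 1.0 to 1.3 mg/dl is assumed.

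- Baseline 0.9: ceiling 2.0 to 2.6 mg/dl, or 2.22 to 2.89 x baseline. Clearance is 45% to 35% of baseline, which is below 40 for any baseline clearance under 88.9 to 115.6 ml/min.
- Baseline 1.0 with ULN 1.2: ceiling 2.4 mg/dl, above the serum hold limit of 2.0.

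**Comparison with the liver rule in the same section.** There the hold needs AST or ALT to double from baseline *and* reach 2 x ULN, so a restart limit joined by 'or' is close to its logical complement. The renal restart sentence has the same form, but the renal hold table has a clearance column, a 1.5 mg/dl limit and no ULN term, so the 'or' loosens it.

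**The case against.** The strongest reply is that a sensitive trigger, a search for the cause and then a discretionary restart is a coherent sequence. A reader might infer that the protocol plainly authorizes redosing at 30 ml/min. It does not go that far: the restart is permissive, and the footnote's hold is not limited to a first occurrence, so it arguably still applies at 30. What stands is that both rules are met by the same patient and the text does not say which governs.

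The second reply is that other controls exist, and they do. In 3.3.2, "Study drug administration must be postponed if a subject develops any Grade 3 or greater adverse event". The same section interrupts dosing while causality is uncertain, and asks the investigator to reconsider treatment after a delay of more than 3 weeks. Section 3.6.1 ends treatment for an event that, in the investigator's opinion, rules out further dosing of either drug. Appendix C holds the study drug or regimen for Grade 2 renal dysfunction and discontinues it at Grade 3 or 4, but it is the durvalumab guideline and its reach to Vicineum is arguable. Under 3.3.1, a subject who cannot tolerate durvalumab leaves protocol therapy, which would end Vicineum too. These lower the risk; none sets a clearance level for restarting Vicineum.

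Third, systemic exposure was small in the Phase 1 study: "Only 2 subjects of 64 had detectable plasma Vicineum levels and these were very near the lower level of quantitation". No text calls 40 ml/min a safety floor for a drug given into the bladder. This supports a low rating. The protocol nevertheless chose that limit for both entry and hold.

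A reader might also take section 14.2.2.3, Table 3 ("Treatment-Emergent Adverse Events Considered Related to Vicineum occurring in") as evidence of renal harm. It is not: its renal and urinary class includes bladder symptoms such as dysuria and urgency, and nothing in it ties an event to low clearance. It should not be used as support.

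**Conclusion.** The inconsistency is real and minor. For any baseline clearance below 80 ml/min, the clearance hold and the restart limit can both be met below 40 ml/min; at 60 ml/min the restart limit reaches down to 30. Two smaller mismatches add to it: the serum overlap for baselines from above 0.75 to below 1.0 mg/dl, and the 2 x ULN alternative.

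The clearance results rest on calculated clearance with stable weight and age; with 24-hour urine collection the halving is approximate. The 2 x ULN figures rest on an assumed ULN. The number of patients affected is unknown and no harm is shown. Endpoints, sample size and error rates are unaffected. A one-sentence tightening of the restart rule, with its follow-on provision, is still worth making.

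**What to change.** Amend the restart sentence in 3.3.2 along these lines: *Once the cause has been evaluated, Vicineum may restart after renal function improves or stabilizes only if creatinine clearance is at least 40 ml/min and the table's serum creatinine hold criterion, judged against the original baseline, is no longer met. If clearance has settled at 40 ml/min or above but is still 25% or more under baseline, the 25% criterion applies from then on to the settled value; the 40 ml/min and serum limits are unchanged.* Add to the table footnote: *except as provided for restart below.*

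The second sentence and the footnote are needed. Without them, a patient falling from 100 to 50 ml/min would again be both held and restartable. Resetting the reference does tolerate a stepwise decline, such as 80 to 60 to 45, but the 40 ml/min and original-baseline serum limits bound it. For the worked patient, the highest creatinine at restart falls from 2.2 mg/dl on the baseline limb to 1.69.

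No new tests are needed, since creatinine is in the acute care panel. The cost falls on patients who settle below 40 ml/min or above the serum limit. They miss instillations that are not made up, each induction week being 1 of 12 (8.3%). Missed doses in the first 6 weeks may also count toward the DLT criterion in 3.1.1 of receiving at least 75% of scheduled treatment: two missed of six Vicineum doses leaves 4/6 = 67%, if counted per drug.

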### 3.4 STUDY CALENDAR

SCHEDULE OF STUDY ASSESSMENTS: Screening (Weeks -12 to -1), Induction Phase (Weeks 1 – 12), and Post-Induction Evaluation (All assessments can be performed within +/- 7 days of scheduled assessment to accommodate holidays and scheduling difficulties)									
Assessments to be performed at the times stipulated in the table and as clinically required in the management of the subject  .	Screening	Baseline	All assessments to be performed pre-infusion unless stated otherwise						Post-Induction and Maintenance
			Week 1	Weeks 2 - 5	Week 6	Weeks 7 - 11	Week 12		
Day	-84 to -1	-7 to 0							
Week	-12 to -1	-1							
Written informed consent/assignment of subject identification number		X							
Inclusion/Exclusion criteria	X								
Demography	X								
Medical and surgical history	X								

SCHEDULE OF STUDY ASSESSMENTS: Screening (Weeks -12 to -1), Induction Phase (Weeks 1 – 12), and Post-Induction Evaluation (All assessments can be performed within +/- 7 days of scheduled assessment to accommodate holidays and scheduling difficulties)									
Assessments to be performed at the times stipulated in the table and as clinically required in the management of the subject  .	Screening	Baseline	All assessments to be performed pre-infusion unless stated otherwise						Post-Induction and Maintenance
			Week 1	Weeks 2 - 5	Week 6	Weeks 7 - 11	Week 12		
Day	-84 to -1	-7 to 0							
Week	-12 to -1	-1							
Previous treatments for bladder cancer including dates/doses of prior BCG	X								
Confirmation of diagnosis by NCI LP	X								
Cystoscopy	X							X (every 3 months as per SCHEMA )	
Bladder biopsies / TURBTs	X							X (every 3 months as indicated as per SCHEMA )	

SCHEDULE OF STUDY ASSESSMENTS: Screening (Weeks -12 to -1), Induction Phase (Weeks 1 – 12), and Post-Induction Evaluation (All assessments can be performed within +/- 7 days of scheduled assessment to accommodate holidays and scheduling difficulties)									
Assessments to be performed at the times stipulated in the table and as clinically required in the management of the subject  .	Screening	Baseline	All assessments to be performed pre-infusion unless stated otherwise						Post-Induction and Maintenance
			Week 1	Weeks 2 - 5	Week 6	Weeks 7 - 11	Week 12		
Day	-84 to -1	-7 to 0							
Week	-12 to -1	-1							
Urine cytology		X						X (every 3 months preceding each cystoscopy as per SCHEMA )	
EpCAM determination		X						Last biopsy on trial	
Tissue PD-L1 assay		X						Last biopsy on trial	
Hepatitis B and C; HIV	X								
Urine hCG or serum $\beta$ hCG 	X 			Week 4		Week 8	X	Prior to each durvalumab dose	

*Abbreviated Title: Durvalumab & Vicineum for NMIBC*

*Version Date: 05/22/2025*

SCHEDULE OF STUDY ASSESSMENTS: Screening (Weeks -12 to -1), Induction Phase (Weeks 1 – 12), and Post-Induction Evaluation (All assessments can be performed within +/- 7 days of scheduled assessment to accommodate holidays and scheduling difficulties)								
Assessments to be performed at the times stipulated in the table and as clinically required in the management of the subject  .	Screening	Baseline	All assessments to be performed pre-infusion unless stated otherwise					
			Week 1	Weeks 2 - 5	Week 6	Weeks 7 - 11	Week 12	Post-Induction and Maintenance
Day	-84 to -1	-7 to 0						
Week	-12 to -1	-1						
Durvalumab administration 				Starting Week 2		Week 6 Week 10		Every 4 weeks resuming in week 15 and as per SCHEMA . Every 3 months if optional maintenance performed after first 12 months.
Vicineum administration 			X	X	X	X	X	Every 2 weeks resuming in week 15 and as per SCHEMA .

SCHEDULE OF STUDY ASSESSMENTS: Screening (Weeks -12 to -1), Induction Phase (Weeks 1 – 12), and Post-Induction Evaluation (All assessments can be performed within +/- 7 days of scheduled assessment to accommodate holidays and scheduling difficulties)									
Assessments to be performed at the times stipulated in the table and as clinically required in the management of the subject  .	Screening	Baseline	All assessments to be performed pre-infusion unless stated otherwise						Post-Induction and Maintenance
			Week 1	Weeks 2 - 5	Week 6	Weeks 7 - 11	Week 12		
Day	-84 to -1	-7 to 0							
Week	-12 to -1	-1							
Physical examination including weight 	X	X		Week 2		Weeks 6, 10	X	Targeted physical examination as needed.	
Vital signs (pre- during and post- durvalumab infusion; pre- and post-Vicineum drainage) 	X	X	All treatment visits						
Electrocardiogram 	X			Week 2		If clinically indicated		If clinically indicated	

**Abbreviated Title:** Durvalumab & Vicineum for NMIBC

**Version Date:** 05/22/2025

SCHEDULE OF STUDY ASSESSMENTS: Screening (Weeks -12 to -1), Induction Phase (Weeks 1 – 12), and Post-Induction Evaluation (All assessments can be performed within +/- 7 days of scheduled assessment to accommodate holidays and scheduling difficulties)									
Assessments to be performed at the times stipulated in the table and as clinically required in the management of the subject  .	Screening	Baseline	All assessments to be performed pre-infusion unless stated otherwise						Post-Induction and Maintenance
			Week 1	Weeks 2 - 5	Week 6	Weeks 7 - 11	Week 12		
Day	-84 to -1	-7 to 0							
Week	-12 to -1	-1							
Adverse event/serious adverse event assessment			All visits						
Concomitant medications		X	All visits						
ECOG performance status	X	X			X				
Acute care panel 	X	X	X	X	X	X	X	Every 2 weeks	
LDH	X	X	X	X	X	X	X	Every 2 weeks	
Pre-albumin		X							
Pancreatic enzymes (amylase, lipase)	X	X	X	X	X	X	X	Every 2 weeks	

**Abbreviated Title:** Durvalumab & Vicineum for NMIBC

**Version Date:** 05/22/2025

SCHEDULE OF STUDY ASSESSMENTS: Screening (Weeks -12 to -1), Induction Phase (Weeks 1 – 12), and Post-Induction Evaluation (All assessments can be performed within +/- 7 days of scheduled assessment to accommodate holidays and scheduling difficulties)									
Assessments to be performed at the times stipulated in the table and as clinically required in the management of the subject  .	Screening	Baseline	All assessments to be performed pre-infusion unless stated otherwise						Post-Induction and Maintenance
			Week 1	Weeks 2 - 5	Week 6	Weeks 7 - 11	Week 12		
Day	-84 to -1	-7 to 0							
Week	-12 to -1	-1							
Hepatic panel	X	X	X	X	X	X	X	Every 2 weeks	
Mineral panel	X	X	X	X	X	X	X	Every 2 weeks	
Thyroid function tests (TSH and fT3 and fT4) 	X	X		Week 2		Week 6 Week 10		Prior to each durvalumab dose	
Hematology 	X	X		Week 2 Week 4	X	Week 8	X	Prior to each durvalumab dose	
Urinalysis	X	X	X	X (weekly)	X	X (weekly)	X	X (prior to each Vicineum treatment)	
Urine culture and sensitivity		X							

SCHEDULE OF STUDY ASSESSMENTS: Screening (Weeks -12 to -1), Induction Phase (Weeks 1 – 12), and Post-Induction Evaluation (All assessments can be performed within +/- 7 days of scheduled assessment to accommodate holidays and scheduling difficulties)									
Assessments to be performed at the times stipulated in the table and as clinically required in the management of the subject  .	Screening	Baseline	All assessments to be performed pre-infusion unless stated otherwise						Post-Induction and Maintenance
			Week 1	Weeks 2 - 5	Week 6	Weeks 7 - 11	Week 12		
Day	-84 to -1	-7 to 0							
Week	-12 to -1	-1							
24 hour urine (only if CrCl to be measured rather than calculated)	X								
PPD testing (if indicated)	X								
Coagulation parameters	X		As clinically indicated						
Urine cytokines		X					X	6 months	
Serum circulating cytokine profile		X		Weeks 2, 3, and 5					

SCHEDULE OF STUDY ASSESSMENTS: Screening (Weeks -12 to -1), Induction Phase (Weeks 1 – 12), and Post-Induction Evaluation (All assessments can be performed within +/- 7 days of scheduled assessment to accommodate holidays and scheduling difficulties)									
Assessments to be performed at the times stipulated in the table and as clinically required in the management of the subject  .	Screening	Baseline	All assessments to be performed pre-infusion unless stated otherwise						Post-Induction and Maintenance
			Week 1	Weeks 2 - 5	Week 6	Weeks 7 - 11	Week 12		
Day	-84 to -1	-7 to 0							
Week	-12 to -1	-1							
sPD-L1 concentration (to assess target engagement)		X		Weeks 2, 3, and 5					
Gene expression analysis		X							
Tissue immune correlates (IHC and possibly RNAseq)		X						Last biopsy on trial	

**Abbreviated Title:** Durvalumab & Vicineum for NMIBC

**Version Date:** 05/22/2025

SCHEDULE OF STUDY ASSESSMENTS: Screening (Weeks -12 to -1), Induction Phase (Weeks 1 – 12), and Post-Induction Evaluation (All assessments can be performed within +/- 7 days of scheduled assessment to accommodate holidays and scheduling difficulties)								
Assessments to be performed at the times stipulated in the table and as clinically required in the management of the subject  .	Screening	Baseline	All assessments to be performed pre-infusion unless stated otherwise					
			Week 1	Weeks 2 - 5	Week 6	Weeks 7 - 11	Week 12	Post-Induction and Maintenance
Day	-84 to -1	-7 to 0						
Week	-12 to -1	-1						
Flow cytometry of PBMCs for immune subsets and antigen-specific responses (T-cell clonal expansion if feasible)		X					X	6 months
Immunogenicity assessment		X				Week 8: ADA	Week 12: AVA	
Tumor CT/CT urogram or MRI/MRI urogram of abdomen and pelvis 	X							Every 12 months while on study

SCHEDULE OF STUDY ASSESSMENTS: Screening (Weeks -12 to -1), Induction Phase (Weeks 1 – 12), and Post-Induction Evaluation (All assessments can be performed within +/- 7 days of scheduled assessment to accommodate holidays and scheduling difficulties)									
Assessments to be performed at the times stipulated in the table and as clinically required in the management of the subject  .	Screening	Baseline	All assessments to be performed pre-infusion unless stated otherwise						Post-Induction and Maintenance
			Week 1	Weeks 2 - 5	Week 6	Weeks 7 - 11	Week 12		
Day	-84 to -1	-7 to 0							
Week	-12 to -1	-1							
Urinary PK for Vicineum		X	X 	X 					
Urinary EpCAM levels		X	X 	X 	X (before Vicineum)	Week 10 (before Vicineum)	X (before Vicineum)		
Follow-up Safety Visits for patients who come off treatment or complete study 								Every month up to 90 days post the last dose of immunotherapy 	

1. May be performed up to 12 weeks prior to enrollment.
2. Pre-menopausal female subjects of childbearing potential only.
3. Dose can be administered within +/- 7 days of scheduled administration to accommodate schedule and holidays.
4. Once weekly intravesical administration for weeks 1-12; Dose can be administered within +/- 7 days of scheduled administration to accommodate schedule and holidays.
5. Full physical examination at screening and/or baseline; targeted physical examination at other timepoints and when clinically indicated.

6. Vital signs will be obtained at a single timepoint at screening and baseline. Subjects will have their blood pressure and pulse measured before, during and after the infusion at the following times (based on a 60-minute infusion):
  - At the beginning of the infusion (at 0 minutes)
  - At 30 minutes during the infusion ( $\pm 5$  minutes)
  - At the end of the infusion (at 60 minutes  $\pm 5$  minutes)
  - In the 1 hour observation period post-infusion: 30 and 60 minutes after the infusion (ie, 90 and 120 minutes from the start of the infusion) ( $\pm 5$  minutes) – for the first infusion only and then for subsequent infusions as clinically indicated.
  - If the infusion takes longer than 60 minutes then blood pressure and pulse measurements should be collected every 30 minutes ( $\pm 5$  minutes) and as described above or more frequently if clinically indicated.
7. ECG during screening required to measure QTc as specified above and 1 ECG is needed while on treatment (pre-durvalumab infusion) and as clinically indicated. ECGs should be obtained after the patient has been in a supine position for 5 minutes and should be recorded while the patient remains in that position. In case of clinically significant ECG abnormalities, including a QTcF value  $>470$  ms, 2 additional 12-lead ECGs should be obtained over a brief period (e.g., 30 minutes) to confirm prolongation. If screening laboratory assessments are performed within 3 days prior to Day 1, they do not need to be repeated at Day 1.
8. Free T3 and free T4 will only be measured if TSH is abnormal. They should also be measured if there is clinical suspicion of an adverse event related to the endocrine system. During maintenance phases 4-7, TSH will be drawn prior to each durvalumab dose and subsequently 4 weeks and 8 weeks after durvalumab administration.
9. Can be given without contrast if severe contrast allergy or renal function does not allow contrast administration per institutional recommendations. MRIs will be done per PI discretion and when clinically indicated.
10. First void after Vicineum administration in Week 1.
11. First void after the next morning after Vicineum administration in Week 1.
12. Day 8 void prior to Vicineum administration in Week 2.
13. H&P, Labs including renal, liver, complete blood count + platelets, coagulation studies monthly for up to 90 days after last immunotherapy.
14. End of treatment visit will occur 90 days after the last dose of immunotherapy. If clinically indicated, patients may continue to be followed by phone or clinic visits beyond that time and up to a year at the NIH/NCI or their local urologist.
15. Per PI discretion, a remote evaluation may be done by phone by a member of the study team. This evaluation will be conducted in compliance with NIH guidelines and FDA regulations. A patient may be asked to come to the NIH Clinical Center or may be referred to their local provider for an in-person assessment, if deemed necessary by the PI. In the case of any visits with participants' local providers, records will be obtained.

